APPENDIX 1 SAMPLE SUBJECT INSTRUCTION SHEET

A sample Subject Instruction Sheet is provided on the next page. The investigator should provide a copy of the Subject Instruction Sheet to each subject and the subject's parent/guardian at Visit 4-LTF prior to dispensing the containers of the test article(s).

SAMPLE SUBJECT AND PARENT/GUARDIAN INSTRUCTION SHEET

Please follow these instructions carefully. If you do not understand anything in these instructions, ask your parent or guardian for help. Contact/ask your parent or guardian to contact the study staff at the telephone number noted below if you have any questions:

Contact: _____ At: _____

THE AREA(S) TO BE TREATED ARE (CIRCLE ALL THAT APPLY): **FACE TRUNK**

STUDY MEDICATION APPLICATION:

- You will be instructed how to apply the cream in the clinic.
- You should apply the cream **TWICE DAILY to your face and/or trunk as directed by the study doctor: once in the morning and once in the evening daily with approximately eight (8) hours or more between applications.**
- Wash the area to be treated with mild soap and water; gently dry.
- Wash your hands before and after applying the cream.
- For your **FACE**:
 - Dispense about 1 gram of cream onto one of your fingertips and then begin to apply the cream to your entire face by dabbing small amounts gently on to multiple facial regions (forehead, cheeks, nose, and chin).
 - Spread the cream evenly with your fingertip to cover your entire face with a very thin even coat of the cream as directed by the study staff.
- For your **TRUNK (optional, to be determined by you and the investigator)**:
 - To cover each 8.5 x 11 inch (~22 x 28 cm) area dispense about 1 gram of cream onto one of your fingertips and then begin to apply the cream to the designated areas of your trunk (shoulders, chest, and back) with acne (as needed) by dabbing small amounts over multiple regions of the area affected with acne.
 - Spread the cream evenly with your fingertip to apply a very thin even coat of the cream over the designated truncal region as directed by the study staff.
- Record date and time of cream application (and areas that were treated) in your subject diary for the face and/or trunk.
- Do not wash the treated area(s) for at least four (4) hours after application or cover or wrap areas where the cream was applied.
- Continue use of the cream as directed by the study doctor.
- If you think your acne has cleared, **DO NOT STOP APPLYING THE CREAM.** Continue to apply the cream and contact the study doctor to be seen in the clinic.

BEFORE EACH STUDY VISIT: Do not apply the cream within 4 hours of your study visit.

ADDITIONAL REMINDERS:

- Store the study medications according to the instructions on the label.
- Bring this sheet, the Subject Diary, and ALL your containers (used and unused) of study medication with you to every study visit.
- Do not allow anyone else to use the study medications and keep the containers of study medication away from children/pets.
- Discontinue use if skin irritation or rash develop and contact the study site.

STUDY VISIT SCHEDULE:

VISIT 5: Date:	Time:	VISIT 6: Date:	Time:
VISIT 8: Date:	Time:	VISIT 10: Date:	Time:

APPENDIX 2 SAMPLE SUBJECT DIARY

A copy of the Subject Diary will be provided to each study site. The investigator should provide a copy of the Subject Diary to each subject and parent/guardian (if applicable) at Visit 4-LTF (Day 1, Baseline) and all follow-up visits, as necessary.

SAMPLE SUBJECT DIARY FOR PROTOCOL CB-03-01/27

Apply the study medication as prescribed. After dosing, record the date and time. If you miss a dose, write MISSED in the space for time. Return this diary AND all tubes of cream (used and unused) at EVERY VISIT. ASK YOUR PARENT/GUARDIAN FOR HELP.

If you have any questions, call NAME: _____ **AT:** _____

Date (dd-   -   -   -yy)	Time of Dose (HH:MM)		Areas Treated	Date (dd-   -   -   -yy)	Time of Dose (HH:MM)		Areas Treated
  /   /  	  :   AM	  :   PM	 Face  Trunk	  /   /  	  :   AM	  :   PM	 Face  Trunk
  /   /  	  :   AM	  :   PM	 Face  Trunk	  /   /  	  :   AM	  :   PM	 Face  Trunk
  /   /  	  :   AM	  :   PM	 Face  Trunk	  /   /  	  :   AM	  :   PM	 Face  Trunk
  /   /  	  :   AM	  :   PM	 Face  Trunk	  /   /  	  :   AM	  :   PM	 Face  Trunk
  /   /  	  :   AM	  :   PM	 Face  Trunk	  /   /  	  :   AM	  :   PM	 Face  Trunk
  /   /  	  :   AM	  :   PM	 Face  Trunk	  /   /  	  :   AM	  :   PM	 Face  Trunk
  /   /  	  :   AM	  :   PM	 Face  Trunk	  /   /  	  :   AM	  :   PM	 Face  Trunk
  /   /  	  :   AM	  :   PM	 Face  Trunk	  /   /  	  :   AM	  :   PM	 Face  Trunk
  /   /  	  :   AM	  :   PM	 Face  Trunk	  /   /  	  :   AM	  :   PM	 Face  Trunk
  /   /  	  :   AM	  :   PM	 Face  Trunk	  /   /  	  :   AM	  :   PM	 Face  Trunk
  /   /  	  :   AM	  :   PM	 Face  Trunk	  /   /  	  :   AM	  :   PM	 Face  Trunk
  /   /  	  :   AM	  :   PM	 Face  Trunk	  /   /  	  :   AM	  :   PM	 Face  Trunk
  /   /  	  :   AM	  :   PM	 Face  Trunk	  /   /  	  :   AM	  :   PM	 Face  Trunk

Site Use Only:	Diary Dispensed at:  Visit 4-LTF  Visit 5  Visit 6	Date Dispensed: _____
	 Visit 8  Visit 10  Unscheduled	Date Returned: _____

APPENDIX 3 TEST ARTICLE INFORMATION

A 3.1 Test Article Packaging and Labeling

The test articles will be packaged and labeled by the Sponsor or designee. CB-03-01 cream, 1% will be packaged in blind-end epoxy lined aluminum tubes, with a polypropylene cap closure, containing 30 grams or 60 grams of the test article. Each subject will be assigned a subject number (carried over from Phase 3 pivotal study [CB-03-01/25 or CB-03-01/26]) and provided with sufficient test article in standard packaging for the designated treatment period during the study.

Tube Labels

Each tube will contain, at a minimum, the following information: the study/protocol number, subject identifiers (e.g., subject number [to be filled in]), the contents, the tube number (to be filled in) with test article batch number), an investigational test article disclaimer (e.g., Caution: New Drug Limited by United States law to investigational use), and the appropriate storage conditions for the test article.

A 3.2 Test Article Storage and Preparation

The test articles will be stored under secure conditions until they are dispensed to the subjects. Test articles should be stored in accordance with the tube labels.

A 3.3 Dispensing Test Article

The test article must be dispensed only to study subjects and only at study sites specified on the form FDA 1572 (or other documents required by the governing national health authority) by authorized personnel as required by applicable regulations and guidelines.

Sufficient test article will be provided to each subject as needed for the designated treatment period. For those subjects with clear facial acne and no truncal acne at Baseline (Visit 4-LTF), the test article will NOT be dispensed and the subject will be reassessed at Visit 5 or earlier (after an unscheduled visit), if acne worsens (be it on the face and/or the trunk) before Visit 5.

As test article is dispensed and collected at clinic visits, tubes will be weighed to the nearest tenth gram (0.1 gram) and information should be recorded on the Study Medication Accountability Log. If treatment is discontinued on the face and trunk, all containers of the test article should be collected. If treatment is re-instated, sufficient test article will be dispensed to the subject; previously returned test article should NOT be re-dispensed, rather new containers of the test article will be dispensed as needed to the subject. Every effort to obtain the return of all dispensed tubes of the test article should be made. If these efforts fail, the reason should be recorded on the drug accountability CRF and a detailed note of the reason for failure should be made in the source documents.

A 3.4 Test Article Supply Records at Study Sites

It is the responsibility of the investigator to ensure that a current record of test article disposition is maintained. Records or logs must comply with applicable regulations and guidelines, and should include:

- Amount received placed in storage area.
- Amount currently in storage area.
- Label ID number (tube numbers).
- Dates and initials of the person responsible for each product inventory entry/movement.
- Amount dispensed to and returned by each subject, including unique subject identifiers.
- Amount transferred to another area for dispensing or storage.
- Non-study disposition (e.g., lost, wasted, broken).
- Amount returned to Sponsor or third party, if applicable.
- Amount destroyed at study site, if applicable.

The CRO will provide forms to facilitate inventory control if the staff at the study site does not have an established system that meets these requirements.

A 3.5 Dose Modifications

The subject should not modify the treatment regimen without consultation with the investigator. If the subject feels that his/her acne has cleared, he/she should continue to apply the test article to the designated treatment area (face and/or trunk) as instructed by the investigator and call the investigator for an unscheduled visit. The subject should NOT change his/her dosing regimen until the investigator has documented acne improvement or worsening to support a change in the treatment recommendations.

Treatment on the face and/or trunk may be discontinued if/when acne clears (achieves an IGA of grade 0 or "minimal" grade 1) and re-instated if/when acne worsens (IGA \geq 2) according to the assessment of the investigator for each respective treatment area.

If skin irritation or rash develops, subject should discontinue use and contact the study site. In the event that the investigator believes dose modification is necessary due to tolerability issues (e.g., problems with tolerance), the subject's care should be discussed with the Medical Monitor prior to making any dose modifications. All dose modifications must be reported on the appropriate CRF.

A 3.6 Documentation of Application and Compliance

A Subject Diary will be dispensed to the subject to record the dates and times of all application doses and any missed doses of the test article ([Appendix 2](#)). Subjects will be

instructed to bring the diary with them to each study visit. The date and time of the first and last application of the test article will be recorded on the appropriate CRF.

A 3.7 Return and Destruction of Test Article Supplies

Upon completion or termination of the study, all test article tubes must be accounted for and any missing tubes of the test article must be explained on the completed Study Medication Accountability Log. All returned tubes will be weighed to the nearest tenth gram (0.1 gram) in order to document extent of subject exposure. Unless instructed otherwise by the Sponsor, the study site will keep the original Study Medication Accountability Log in the study file. A copy of the Study Medication Accountability Log will be returned to the Sponsor. All tubes of test article will then either be a) returned to the study Sponsor or b) emptied and provided to a sponsor-identified third party vendor for appropriate destruction, according to applicable regulations with the provision of a certificate of destruction.

**STUDY SCHEDULE**

Visit	Visits 1-4 Pivotal Phase 3	Visit 4-LTF Baseline	Visit 5	Visit 6	Visit 7 Phone Call 1	Visit 8	Visit 9 Phone Call 2	Visit 10  EOS	Unscheduled
Long-Term Follow-Up (LTF): Month Day		0 1	1 29 ± 10	3 85 ± 15	4.5 137 ± 15	6 183 ± 15	7.5 228 ± 15	9 274 ± 21	If/As Needed
Overall CB-03-01 Exposure: Month	0 or 3	0 or 3	1 or 4	3 or 6	4.5 or 7.5	6 or 9	7.5 or 10.5	9 or 12	
PROCEDURES	See Phase 3								
Informed Consent/Assent 		X 							
Inclusion/Exclusion Criteria		X							
Demographics		From Phase 3 							
Medical/Dermatological History		From Phase 3 							
Physical Exam with Vital Signs		X							
UPT for WOCBP		X 				X		X	
IGA (Face and Trunk, separately)		Face: From Phase 3  Trunk: X 	X	X		X		X	X
Determination of Test Article Dosing		X	X	X		X		X	X
LSRs Assessment (Face and Trunk, separately)		X 	X	X		X		X	X
AEs		X	X	X	X	X	X	X	X
Concomitant Medications & Procedures		From Phase 3 	X	X	X	X	X	X	X
Dispense & Collect ITA 		X	X	X		X		X	X
Review of Compliance			X	X	X	X	X		X

- 1 Subjects who terminate early shall complete all final visit activities.
- 2 For this LTF study, subjects must rollover from the Phase 3 pivotal study (CB-03-01/25 and CB-03-01/26) into this study AT or WITHIN THREE (3) DAYS of Visit 4-Pivotal.
- 3 Given that the Phase 3 pivotal trial is randomized (1:1) between active (CB-03-01 cream, 1%) and vehicle, upon entering the LTF study, some subjects had an overall exposure to CB-03-01 cream, 1% of 3 months and others had 0 months (i.e., subjects were treated with vehicle in the Pivotal study).
- 4 Consent/assent may be performed up to 45 days prior to the Baseline Visit.
- 5 Demographics and medical/dermatological history were used from the Phase 3 pivotal study (Visit 1-Pivotal).
- 6 If Visit 4-Pivotal and Visit 4-LTF occur on the same day, the results of the UPT performed during the End of Study (EOS) visit of the Phase 3 pivotal study can be used as Baseline data.
- 7 IGA performed at the EOS Visit of the Phase 3 pivotal trial were used as Baseline data (Visit 4-Pivotal).
- 8 If truncal acne is to be treated (as designated by the investigator AND desired by subject), identify the percent body surface area (BSA) to be treated. BSA was estimated based on the assumption that 1% BSA is equivalent to the area of the subject's hand with fingers held together.
- 9 LSRs assessed at the EOS Visit of the Phase 3 pivotal trial (Visit 4-Pivotal) were used as pre-application data for face. LSRs [pre-application] were assessed for trunk at Visit 4-LTF. After ITA application in the clinic, LSRs were assessed post-application (Visit 4-LTF) for face and trunk, as applicable.
- 10 Any ongoing concomitant medications and procedures were reviewed at Visit 4-LTF.
- 11 Instruct subject (and parent/guardian, if applicable) on ITA application and provide instruction sheet. Review compliance with respect to the amount and number of doses applied since the last visit.
- 12 Dispense subject diary, as needed.

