Study Procedures	
The study will consist of a Baseline Visit, follow-up visits at LTF-Months 1, 3, 6, and 9, and follow-up phone calls at LTF-Months 4.5 and 7.5. For subjects in the Phase 3 pivotal studies randomized to active (CB-03-01 cream, 1% twice daily), the total treatment period will be 12 (3+9) months; whereas for those subjects in the Phase 3 pivotal studies randomized to vehicle, the total treatment period will be 9 (0+9) months.
 
For this Long-Term Follow-Up (LTF) study, subjects must rollover from the Phase 3 pivotal study (CB-03-01/25 and CB-03-01/26) into this study AT or WITHIN THREE (3) DAYS of Visit 4-Pivotal.
 
During the LTF study, subjects will treat facial acne per protocol for nine months. Treatment of truncal acne is optional and will be discussed by the investigator and subject (see Section 10.3). If truncal acne is to be treated, the subject must continue to treat the designated treatment area for the remainder of the study as detailed in Section 6.2. Treatment on face and/or trunk for a subject may be discontinued if/when acne is under successful control (achieves an IGA of grade 0 or “minimal” grade 1) and re-instated if/when acne worsens (IGA ≥ 2) according to the assessment of the investigator for each respective treatment area. Subjects must be seen by the investigator via a scheduled or unscheduled visit to change (i.e., restart or stop) test article dosing. Acne will be managed per protocol as detailed in Section 6.2 and Section 8.2.
 
Visit 4-LTF (Baseline): At Visit 4-LTF, study staff will explain the study procedures and an informed consent/assent must be signed prior to the initiation of any study-related procedures. At this visit, inclusion/exclusion criteria will be reviewed to determine subject eligibility. Demographics and medical/dermatological history data will be used from the Phase 3 pivotal study. A brief physical examination including vital signs and a UPT (if applicable) will be performed. Note: If Visit 4-Pivotal and Visit 4-LTF occur on the same day, the results of the UPT performed during the End of Study (EOS) visit of the Phase 3 pivotal study can be used as Baseline data. IGA for the face and local skin reactions (LSRs) [pre-application for the face] performed during the EOS Visit of the Phase 3 pivotal study (Visit 4-Pivotal) will be used as Baseline data. Treatment of truncal acne will be discussed by the investigator and subject. If the subject desires, the truncal treatment area will be defined and agreed upon by the investigator and the subject, with the percent body surface area (BSA) to be treated recorded. If the investigator

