Visit	Visits 1-4 Pivotal Phase 3	Visit 4-LTF Baseline	Visit 5	Visit 6	Visit 7 Phone Call 1	Visit 8	Visit 9 Phone Call 2	Visit 10 ¹ EOS	Unscheduled
Long-Term Follow-Up (LTF): Month Day		0 1²	1 29 \pm 10	3 85 \pm 15	4.5 137 \pm 15	6 183 \pm 15	7.5 228 \pm 15	9 274 \pm 21	If/As Needed
Overall CB-03-01 Exposure: Month³	0 or 3	0 or 3	1 or 4	3 or 6	4.5 or 7.5	6 or 9	7.5 or 10.5	9 or 12	
PROCEDURES	See Phase 3								
Informed Consent/Assent ⁴		X ⁴							
Inclusion/Exclusion Criteria		X							
Demographics		From Phase 3 ⁵							
Medical/Dermatological History		From Phase 3 ⁵							
Physical Exam with Vital Signs		X							
UPT for WOCBP		X ⁶				X		X	
IGA (Face and Trunk, separately)		Face: From Phase 3 ⁷ Trunk: X ⁸	X	X		X		X	X
Determination of Test Article Dosing		X	X	X		X		X	X
LSRs Assessment (Face and Trunk, separately)		X ⁹	X	X		X		X	X
AEs		X	X	X	X	X	X	X	X
Concomitant Medications & Procedures		From Phase 3 ¹⁰	X	X	X	X	X	X	X
Dispense & Collect ITA ^{11,12}		X	X	X		X		X	X
Review of Compliance			X	X	X	X	X		X

¹ Subjects who terminate early shall complete all final visit activities.

² For this LTF study, subjects must rollover from the Phase 3 pivotal study (CB-03-01/25 and CB-03-01/26) into this study AT or WITHIN THREE (3) DAYS of Visit 4-Pivotal.

³ Given that the Phase 3 pivotal trial is randomized (1:1) between active (CB-03-01 cream, 1%) and vehicle, upon entering the LTF study, some subjects will have an overall exposure to CB-03-01 cream, 1% of 3 months and others will have 0 months (i.e., subjects were treated with vehicle in the Pivotal study).

⁴ Consent/assent may be performed up to 45 days prior to the Baseline Visit.

⁵ Demographics and medical/dermatological history will be used from the Phase 3 pivotal study (Visit 1-Pivotal).

⁶ If Visit 4-Pivotal and Visit 4-LTF occur on the same day, the results of the UPT performed during the End of Study (EOS) visit of the Phase 3 pivotal study can be used as Baseline data.

⁷IGA performed at the EOS Visit of the Phase 3 pivotal trial will be used as Baseline data (Visit 4-Pivotal).

⁸ If truncal acne is to be treated (as designated by the investigator AND desired by subject), identify the percent body surface area (BSA) to be treated. BSA will be estimated based on the assumption that 1% BSA is equivalent to the area of the subject's hand with fingers held together.

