14.1 Adverse Event (AE)

All AEs must be recorded on the AE CRF. AEs should be followed to resolution or stabilization (if possible), and reported as serious adverse events (SAEs) if they become serious.

LSRs that have been reported in subjects treated with CB-03-01 creams (0.1%-1% concentration) include (with decreasing frequency) erythema, pruritus, scaling/dryness, skin atrophy, striae rubrae, stinging/burning, edema, and telangiectasia; however most LSRs were typically of minimal to mild severity. No subjects discontinued treatment due to these LSRs.

AEs that have been reported in subjects treated with CB-03-01 creams (0.1-1% concentration) were minimal, typically mild in severity, and most were recovered/resolved without sequelae at the end of the study. Only two AEs in one (1) subject were judged as probably or possibly related to treatment; both of these treatment-related AEs (burning and cold at application site) were mild in severity. Two SAEs have been reported to date; both were not related to treatment and were resolved at the end of the study. In addition, one subject discontinued early from the study due to an AE (urinary tract infection), which was not related to treatment.

The investigator will instruct the subject to report any AEs that may occur during the study. At each visit, the investigator should ask the subject, in non-directive fashion, about any change in the subject's overall condition since the previous visit.

The severity of each AE, as judged by the investigator, will be recorded on the appropriate AE CRF and will be graded according to the following scale:

Mild - The AE is transient and easily tolerated by the subject.

Moderate - The AE causes the subject discomfort and interrupts the subject's usual activities.

Severe - The AE causes considerable interference with the subject's usual activities, and may be incapacitating or life-threatening.

The investigator must determine the relationship of the AE to the test article according to the following categories:

Definite - An event that follows a reasonable temporal sequence from administration of the test article; that follows a known or expected response pattern to the test article; and that is confirmed by improvement on stopping or reducing the dosage, and reappearance of the event on repeated exposure (re-challenge).

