17.3.2 Efficacy Analyses

Investigator's Global Assessment (IGA)

Frequency distributions of IGA scores will be summarized at Baseline (EOS-Pivotal), and LTF Months 1, 3, 6, and 9 for face and trunk, separately.

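### The face Baseline column for LSRs and IGA pools subjects with 0 and with 3 months of CB-03-01, and no split by prior pivotal arm is planned

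*SAP*

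**What the plan says.** **Source of the face Baseline.** For face LSRs, the SAP Study Schedule, footnote 9, says: "LSRs assessed at the EOS Visit of the Phase 3 pivotal trial (Visit 4-Pivotal) were used as pre-application data for face". Footnote 7 and SAP 3.1 take the face IGA from the same visit. The protocol synopsis (Study Procedures) gives both measures the same Baseline source: "IGA for the face and local skin reactions (LSRs) [pre-application for the face] performed during the EOS Visit of the Phase 3 pivotal study". Trunk values are taken at Visit 4-LTF, or when trunk treatment first starts, so this point concerns the face only.

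**Exposure at that visit.** SAP schedule footnote 3 explains that the "Phase 3 pivotal trial is randomized (1:1) between active (CB-03-01 cream, 1%) and vehicle", and that on entry "some subjects had an overall exposure to CB-03-01 cream, 1% of 3 months and others had 0 months".

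**Planned summaries.** SAP 6.1.1 and 7.9.1 give the frequency and severity of each LSR at each visit. SAP 6.1.2 and 7.6 give the number of subjects with each IGA score at each time point, in contingency tables. Baseline is one time point among several. Neither document describes a change-from-Baseline analysis or a rule counting only reactions new since Baseline. SAP 6.2 plans no hypothesis test. SAP 7.7 and Protocol 17.4 plan no subgroup analysis.

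**Prior experience.** Protocol 14.1 says: "LSRs that have been reported in subjects treated with CB-03-01 creams (0.1%-1% concentration) include (with decreasing frequency) erythema, pruritus, scaling/dryness, skin atrophy, striae rubrae". The list goes on to telangiectasia. Protocol Section 2 puts use up to then at no more than 12 weeks.

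**The concern.** The plan runs two clocks. Exposure is counted from the first CB-03-01 dose: the 6-month and 12-month targets include the pivotal months, and SAP 7.5.3 tabulates subjects on-study at 3, 6, 9 and 12 months. Face skin status is counted from rollover. For prior-vehicle subjects the two clocks agree. For prior-active subjects, the only ones who can reach 12 months, the Baseline value is a Month 3 on-drug value, although footnote 9 calls it pre-application. Demographics and medical history, by contrast, come from Visit 1-Pivotal.

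The study is open-label with a single treatment. A reader who asks whether atrophy, striae or telangiectasia became more common with long use will set later visits against the Baseline column, because nothing else is on the page. That column mixes two exposure states, and the SAP text describes no way to separate them.

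The adverse event tables are unlikely to fill the gap. Under Protocol 10.2 and SAP 3.2, a listed LSR becomes an adverse event only if it needs medical intervention or withholding of the cream. Milder atrophy or striae that arose during the pivotal study would show only in the LSR table, inside Baseline.

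**Working it through.** **1. The plan's own exposure row.** Total exposure is the LTF month plus 0 (prior vehicle) or plus 3 (prior active).

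| LTF month | 0 | 1 | 3 | 4.5 | 6 | 7.5 | 9 |
|---|---|---|---|---|---|---|---|
| Prior vehicle | 0 | 1 | 3 | 4.5 | 6 | 7.5 | 9 |
| Prior active | 3 | 4 | 6 | 7.5 | 9 | 10.5 | 12 |

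This reproduces the schedule exactly. Every pooled column mixes two exposures three months apart. Only at LTF month 0 is one of them zero.

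**2. Subjects affected.** SAP 2.5 reports 609 subjects. The 1:1 ratio is the pivotal randomisation; the split among rollover subjects is not given. Let s be the prior-active share, assumed to lie between 40% and 60%. Then 609 × 0.4 = 243.6, 609 × 0.5 = 304.5 and 609 × 0.6 = 365.4, or about 244 to 365 subjects with an on-drug Baseline.

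**3. Effect on a Baseline-to-later reading.** For one LSR, let p0 be the prevalence before CB-03-01, p3 the prevalence after 3 months on drug, and pL the prevalence at a later LTF visit.

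- Pooled Baseline = s·p3 + (1 − s)·p0
- True rise = pL − p0
- Visible rise = pL − pooled Baseline
- Shortfall = true rise − visible rise = s·(p3 − p0)

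If the on-drug level is reached by Month 3 and then holds (p3 = pL = p1), the visible rise is (1 − s)·(p1 − p0). The fraction shown is 1 − s, whatever p0 and p1 are. With assumed values p0 = 2% and p1 = 6%, the true rise is 4.0 points:

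| s | Pooled Baseline | Visible rise | Fraction shown |
|---|---|---|---|
| 40% | 3.6% | 2.4 points | 60% |
| 50% | 4.0% | 2.0 points | 50% |
| 60% | 4.4% | 1.6 points | 40% |

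Within prior-active subjects alone the visible rise is p1 − p1 = 0.

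**4. If prevalence keeps rising after Month 3.** Assume p0 = 1%, p3 = 4% and pL = 6%, a true rise of 5 points. With s = 50%, the pooled Baseline is 2.5% and the visible rise 3.5 points (70% shown). With s = 40% the visible rise is 3.8 points (76%), and with s = 60% it is 3.2 points (64%). Within prior-active subjects it is 6 − 4 = 2 points (40%). If nothing arises by Month 3 (p3 = p0), the shortfall is zero.

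**5. What does not change.** pL appears in full in the later-visit column in every case. Only the difference between columns is affected.

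**The case against.** The strongest reply is that no planned analysis uses Baseline as a reference. A reader might infer that reactions present at Visit 4-Pivotal drop out of the later counts. They do not: the summaries are absolute, and a reaction that persists is counted again at each visit. The IGA is a static scale, explicitly not relative to Baseline. This stands, and it limits the point to how the tables will be read. The IGA contingency tables might cross visits with Baseline, but the table shells are not available to check.

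Second, the choice is disclosed. The exposure row prints 0 or 3 months at Baseline, Protocol 17.3.2 labels the IGA column as the end of the pivotal study, and the objective speaks of nine additional months. Baseline at rollover is a reasonable choice for an extension study. This also stands. But the same objective runs to 12 months in total, and the pooled table cannot show local change over that period.

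Third, a reader might infer from Protocol 14.1 that the drug is known to have caused skin changes by Month 3. The documents do not support that. The section gives no rates and no vehicle comparison, describes most reactions as minimal to mild, and reports no discontinuation because of them. SAP 3.2 links erythema, edema and scaling to acne itself.

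Fourth, it is tempting to redefine Baseline by arm as the last value before CB-03-01. That would pool scores taken before any study cream with scores taken after three months of vehicle, and it would depart from the protocol's definition. It is not the remedy.

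**Conclusion.** The point holds as one of presentation and interpretation. The face Baseline for LSRs and IGA pools subjects before any CB-03-01 with subjects three months into it, and the SAP text plans no split by prior arm. No planned count is wrong and no endpoint is miscomputed. What suffers is the comparison that readers of an uncontrolled study will naturally make.

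The size is unknown because the documents give no LSR rates. The fraction shown, 60% to 40% for an assumed prior-active share of 40% to 60%, requires that the on-drug level is reached by Month 3 and then stays level. It also assumes that the prior-active share is the same at later visits, that both arms started from the same prevalence, and that vehicle alone does not change it. A later-developing effect loses less. The percentages should be read as the behaviour of the pooled column under stated assumptions, not as an estimate of bias in a planned result. The documents do not support saying that the plan conceals drug reactions or that its Baseline definition is an error.

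**What to change.** Keep the protocol's Baseline definition and change the display.

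- In SAP 7.6 and 7.9.1, present the face IGA and face LSR tables by prior pivotal treatment (active or vehicle), with total CB-03-01 exposure shown for each visit.
- Label Visit 4-Pivotal *on drug, Month 3* for prior-active subjects and *before CB-03-01* for prior-vehicle subjects.
- Add a Visit 1-Pivotal column for both groups if face LSR and IGA scores were collected then. The documents do not say whether they were. If they were not, state in the table note that prior-active subjects have no drug-free face reference.
- Record the split as an exception to SAP 7.7. Because Protocol 17.4 also plans no subgroups, mention it in SAP 1.1 too.

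The cost is a few more table columns and a merge of pivotal-study data, made easier because subject numbers carry over. No new data collection is needed.
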